9.4. Abnormal Test Findings

The criteria for determining whether an abnormal objective test finding should be reported as an AE are as follows:

- Test result is associated with accompanying symptoms, and/or
- Test result requires additional diagnostic testing or medical/surgical intervention, and/or
- Test result leads discontinuation from the study, significant additional concomitant drug treatment, or other therapy, and/or
- Test result is considered to be an AE by the investigator or Sponsor.

Merely repeating an abnormal test, in the absence of any of the above conditions, does not constitute an AE. Any abnormal test result that is determined to be an error does not require reporting as an AE.

9.5. Serious Adverse Events

An SAE is any untoward medical occurrence at any dose that:

- Results in death (not due to disease progression);
- Is life-threatening (immediate risk of death);
- Requires inpatient hospitalization or prolongation of existing hospitalization;
- Results in persistent or significant disability/incapacity (substantial disruption of the ability to conduct normal life functions);
- Results in congenital anomaly/birth defect;
- Is determined to be an important medical event by the study investigator.

Medical and scientific judgment is exercised in determining whether an event is an important medical event. An important medical event may not be immediately life-threatening and/or result in death or hospitalization. However, if it is determined that the event may jeopardize the patient or may require intervention to prevent one of the other AE outcomes, the important medical event should be reported as serious.

Examples of such events are intensive treatment in an emergency room or at home for allergic bronchospasm; blood dyscrasias or convulsions that do not result in hospitalization; or development of drug dependency or drug abuse.

9.5.1. Adverse Events of Special Interest

Abnormal values in AST and/or ALT concurrent with abnormal elevations in total bilirubin that meet the criteria outlined below in the absence of other causes of liver injury are considered potential cases of drug-induced liver injury (potential Hy's Law cases) and should always be considered important medical events.

The threshold of laboratory abnormalities for a potential case of drug-induced liver injury depends on the patient's individual baseline values and underlying conditions. Patients who

present with the following laboratory abnormalities should be evaluated further to definitively determine the etiology of the abnormal laboratory values:

- Patients with AST or ALT and total bilirubin baseline values within the normal range who subsequently present with AST or ALT ≥ 3 times the upper limit of normal (X ULN) concurrent with a total bilirubin ≥ 2 X ULN with no evidence of hemolysis and an alkaline phosphatase ≤ 2 X ULN or not available.
- For patients with preexisting ALT **OR** AST **OR** total bilirubin values above the upper limit of normal, the following threshold values should be used in the definition mentioned above:
 - For patients with pre-existing AST or ALT baseline values above the normal range: AST or ALT ≥ 2 times the baseline values and ≥ 3 X ULN, or ≥ 8 X LLN (whichever is smaller).
- **Concurrent with**
 - For patients with pre-existing values of total bilirubin above the normal range: Total bilirubin increased by one time the upper limit of normal **or** ≥ 3 times the lower limit of normal (whichever is smaller).

The patient should return to the investigational site and be evaluated as soon as possible, preferably within 48 hours from awareness of the abnormal results. This evaluation should include laboratory tests, detailed history and physical assessment. For oncology studies, the possibility of hepatic neoplasia (primary or secondary) should be considered. In addition to repeating AST and ALT, laboratory tests should include albumin, creatine kinase, total bilirubin, direct and indirect bilirubin, gamma-glutamyl transferase, prothrombin time (PT)/INR, and alkaline phosphatase. A detailed history, including relevant information, such as review of ethanol, acetaminophen, recreational drug and supplement consumption, family history, occupational exposure, sexual history, travel history, history of contact with a jaundiced patient, surgery, blood transfusion, history of liver or allergic disease, and work exposure, should be collected. Further testing for acute hepatitis A, B, or C infection and liver imaging (eg, biliary tract) may be warranted. All cases confirmed on repeat testing as meeting the laboratory criteria defined above, with no other cause for LFT abnormalities identified at the time should be considered potential Hy's Law cases irrespective of availability of all the results of the investigations performed to determine etiology of the abnormal LFTs. Such potential Hy's Law cases should be reported as SAEs.

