4.1. Inclusion Criteria

Patients must meet all of the following inclusion criteria to be eligible for enrollment into the study:

1. Patient has been informed of the investigational nature of this study and has given written informed consent in accordance with institutional, local, and national guidelines;
2. Age \geq 20 years old;
3. Life expectancy of at least 12 weeks;
4. **Phase 1b:** No prior chemotherapy or radiotherapy for advanced gastric or GEJ cancer within 6 months prior to Day 0;
5. **Phase 2/Phase 2 Extension:** No prior chemotherapy or radiotherapy for advanced gastric or GEJ cancer within 3 months prior to Day 0;
6. Metastatic gastric or GEJ adenocarcinoma, or locally advanced disease not amenable to surgical resection;
7. HER2/neu overexpression (3+ by immunohistochemistry (IHC) or if IHC 2+ confirmed by fluorescent in situ hybridization [FISH], brightfield double in situ hybridization [BDISH] or chromogenic in situ hybridization [CISH]). Patients with IHC 2+ expression without confirmation of overexpression by fluorescent in situ hybridization [FISH], brightfield double in situ hybridization [BDISH] or chromogenic in situ hybridization [CISH]) may be included in Phase 1b with agreement of Imugene Limited;
8. **Phase 1b:** ECOG performance status 0–1;
9. **Phase 2/Phase 2 Extension:** ECOG performance status 0–2;
10. At least one measurable lesion as defined by RECIST 1.1 criteria. Patients with non-measurable lesions may be included in Phase 1b with agreement of Imugene Limited.;
11. Adequate left ventricular ejection function at baseline, defined as LVEF $> 50\%$ by echocardiogram or MUGA scan (Multi Gated Acquisition Scan);
12. Adequate hematologic function: absolute neutrophil count (ANC) $\geq 1.5 \times 10^9/L$, platelet count $\geq 100 \times 10^9/L$, and hemoglobin $\geq 9 \text{ g/dL}$;
13. Adequate liver function evidenced by bilirubin $\leq 1.5 \times$ laboratory upper limit of normal [ULN], and ALT and AST $\leq 3 \times$ laboratory ULN if no liver involvement or ALT and AST ≤ 5 times laboratory ULN with liver involvement;
14. Adequate renal function (creatinine $\leq 1.5 \times$ laboratory ULN);

Investigational Product: IMU-131
Protocol Identifier: IMU.ACS.001
Protocol Version: Protocol Global Amendment #5, 27 September 2023

15. Willing and able to comply with scheduled visits, treatment plan, laboratory tests, and other study procedures.

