8.6. Phase 2 and Phase 2 Extension Laboratory Assessments

Hematology and serum chemistry analyses will be performed by an accredited local laboratory. Serum predication markers of tumor progression and intra-tumor T cell and biomarker analysis will be performed by an accredited central laboratory. Humoral and cellular immunological analysis will be performed by an accredited specialist central immunology laboratory.

Unused blood /serum and/or tissue samples collected during the study from patients who have signed an appropriate informed consent form may be stored and used for future research. The coded samples may be stored up to 15 years after the clinical study ends. A patient may contact the investigator to have their unused samples destroyed at any time

Investigational Product: IMU-131
Protocol Identifier: IMU.ACS.001
Protocol Version: Protocol Global Amendment #5, 27 September 2023

during the storage period. Results from the future use studies will not be shared with patients.

1) Safety Laboratory Assessments (Screening, Baseline, Days 21, 42, 63, 84, 105, 126 then every 42 days and EoT visit)

Blood samples of approximately 10 mL per visit for the assessment of hematological and serum chemistry parameters will be collected and processed in accordance with local laboratory procedures and reference ranges.

Safety laboratory panels are defined as follows:

Human immunodeficiency virus (HIV 1/2 antibodies), hepatitis B (HBsAg reactive) and hepatitis C (HCV ribonucleic acid [RNA] qualitative) (at screening only).

Hematology: Hematology to include CBC, including RBC count, hemoglobin, hematocrit, reticulocyte count, WBC count with differential (neutrophils, bands, eosinophils, basophils, lymphocytes, monocytes, and other cells), platelet count, and C-reactive protein (CRP).

Serum Chemistry: BUN or urea, creatinine, sodium, chloride, potassium, magnesium, bicarbonate, calcium, phosphorus, total protein, albumin, alkaline phosphatase, glucose, total bilirubin, direct and indirect bilirubin, lactate dehydrogenase (LDH), cholesterol, uric acid, triglyceride levels, gamma glutamyl transpeptidase (GGT), AST, and ALT.

2) Exploratory Endpoint Laboratory Assessments (Baseline, Days 84 then every 84 days and EoT visit)

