9.2. Reporting Period

For AEs/SAEs, the active reporting period to Imugene Limited or its designated representative begins from the time that the patient provides informed consent, which is obtained prior to the patient's participation in the study, i.e., prior to undergoing any study-related procedure and/or receiving investigational product, through and including 28 calendar days after the last administration of the investigational product, including administration during long term maintenance. After informed consent has been obtained but prior to initiation of study drug(s), only SAEs caused by a protocol-mandated intervention (e.g., invasive procedures such as biopsies, discontinuation of medications) should be reported.

The cause of death must be reported as an SAE if it occurs at any time after the SAE reporting period and is likely to be related to the investigational product.

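### Protocol 9.5.1 bases the raised-baseline Hy's Law limits on the lower limit of normal, so a patient with stable liver tests can meet both

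*Protocol*

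**What the plan says.** Protocol 9.5.1 defines a potential Hy's Law case. With normal baselines, the patient needs AST or ALT at 3 × ULN or more together with total bilirubin at 2 × ULN or more, "with no evidence of hemolysis and an alkaline phosphatase" no higher than 2 × ULN (or missing).

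For raised baselines, two limits are substituted:

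- AST/ALT: at least twice baseline and at least 3 × ULN, or at least "8 X LLN (whichever is smaller").
- Bilirubin: a rise of 1 × ULN, or at least 3 "times the lower limit of normal (whichever is smaller").

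LLN is in the list of abbreviations as the lower limit of normal, and the bilirubin limit spells it out, so this is not a text-extraction fault.

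Section 4.1 admits patients with bilirubin up to 1.5 × ULN and AST/ALT up to 3 × "laboratory ULN if no liver involvement or ALT and AST" up to 5 × ULN with it. Both tests can therefore be raised at entry. Under 9.5.1, cases "confirmed on repeat testing as meeting the laboratory criteria defined above" with no other cause found are potential Hy's Law cases, and such "Law cases should be reported as SAEs".

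**The concern.** A rule for raised baselines should ask for a change beyond a value that is already abnormal. This one can set a lower bar than the rule for normal baselines, and one that the entry value may already clear. Repeat testing does not screen out a stable patient, because a stable value confirms itself.

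At stake is the meaning of the liver safety signal: work-ups preferably within 48 hours, and serious adverse event reports, in patients whose liver tests have not moved. Before study drug, "only SAEs caused by a protocol-mandated intervention" are reportable (Protocol 9.2), so the problem begins with on-treatment laboratory tests rather than at Day 0. After Day 0 these are first scheduled at Day 21 in Phase 2 and its Extension (Protocol 8.6) and at Day 14 in Phase 1b (Protocol 7.5.1).

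**Working it through.** **Inputs.** The limits come from Protocol 9.5.1 and the entry caps from Protocol 4.1. The ratio R = ULN/LLN is an assumption, because no reference ranges are given and Phase 2 uses local laboratory ranges. R may differ between tests and sites. Let b be baseline AST/ALT and c baseline bilirubin, both in multiples of ULN.

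**As written, natural reading** (8 × LLN stands alone as an alternative):

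- AST/ALT limit = min(max(2b, 3), 8/R)
- Bilirubin limit = min(c + 1, 3/R)

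Since max(2b, 3) is at least 3, and 8/R is below 3 once R exceeds 8/3 = 2.67, the doubling condition never operates above that ratio. Since 3/R is at most 1 for R ≥ 3, every raised bilirubin then meets its limit unchanged.

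| R | AST/ALT limit, 8/R (× ULN) | Bilirubin limit, 3/R (× ULN) |
|---|---|---|
| 3 | 2.67 | 1.00 |
| 4 | 2.00 | 0.75 |
| 5 | 1.60 | 0.60 |
| 8 | 1.00 | 0.375 |

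**Example.** Take b = 2.5 and c = 1.2, eligible even without liver involvement. At R = 4 the limits are min(5, 2.00) = 2.00 and min(2.2, 0.75) = 0.75, both met with no change. At R = 3 they are 2.67 and 1.00, and only bilirubin is met.

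**Smaller ratios.** Unchanged eligible values can meet the bilirubin limit only if 3/R ≤ 1.5, that is R ≥ 2. They can meet the AST/ALT limit only if 8/R ≤ 5 (R ≥ 1.6) with liver involvement, or 8/R ≤ 3 (R ≥ 2.67) without.

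**One test raised.** The other test keeps its normal-baseline limit (3 × ULN or 2 × ULN), so unchanged values cannot complete the definition.

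**Alternative reading** (doubling always required, plus the smaller fixed limit): AST/ALT limit = max(2b, min(3, 8/R)). Unchanged AST/ALT no longer qualifies because 2b exceeds b. The bilirubin limit is still met unchanged, so an AST/ALT rise alone completes the definition. At R = 4, AST going from 1.5 to 3.0 × ULN meets max(3.0, 2.0) = 3.0, with bilirubin steady at 1.2 against 0.75.

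**With ULN for LLN:** AST/ALT limit = min(max(2b, 3), 8) and bilirubin limit = min(c + 1, 3). The example gives 5.0 and 2.2. At the caps (b = 5, c = 1.5) the limits are 8.0 and 2.5. No eligible value meets either limit unchanged, since 2b > b, 8 > 5, c + 1 > c and 3 > 1.5.

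**Grid over the entry range with both raised** (b from 1.01 to 5.00 and c from 1.01 to 1.50, steps of 0.01: 400 × 50 = 20,000 points). Points meeting both limits unchanged on the natural reading:

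| R | All b | b ≤ 3.00 only (10,000 points) |
|---|---|---|
| 3 | 234 × 50 = 11,700 | 34 × 50 = 1,700 |
| 4 | 301 × 50 = 15,050 | 101 × 50 = 5,050 |
| 5 | 341 × 50 = 17,050 | 141 × 50 = 7,050 |
| 8 | 400 × 50 = 20,000 | 200 × 50 = 10,000 |

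With the corrected rule the count is 0. The counts describe the range of eligible values, not a share of patients.

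**The case against.** The strongest reply is that the limits do not act alone. Other causes of liver injury must be absent, the section tells investigators to consider liver tumor, and a stable elevation that predates study drug itself suggests another cause. AST/ALT above 3 × ULN is eligible only with liver involvement, and those values make up much of the grid: 10,000 of 11,700 points at R = 3, and 10,000 of 15,050 at R = 4. This stands as a limit on frequency. It makes false reports possible rather than certain, but it leaves the correction to case-by-case judgment. The b ≤ 3.00 column shows that patients without liver involvement are exposed too.

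Second, the error can only over-capture. On the natural reading min(x, 8/R) ≤ min(x, 8) for any R ≥ 1, and likewise for bilirubin, so every case the corrected rule would flag is flagged already. This stands: no liver signal is lost.

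Third, R is assumed and the AST/ALT sentence can be read two ways. This also stands for the claim about unchanged values on both limbs, but the bilirubin fault survives either reading.

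Fourth, 8 × ULN and 3 × ULN appear nowhere in the documents as raised-baseline limits, so the replacement is inferred. That is why the medical lead should confirm it.

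**Conclusion.** The concern holds. The raised-baseline limits in Protocol 9.5.1 are wrong as written, and LLN is probably a slip for ULN. That inference rests on the ULN basis of the normal-baseline rule and on the fact that the substitution restores a coherent rule.

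For R of 3 or more, every raised bilirubin meets its limit unchanged. With bilirubin raised, the lowest baseline AST/ALT that completes the definition unchanged is 2.67, 2.00 or 1.60 × ULN at R = 3, 4 or 5, and any raised value at R = 8. This assumes the natural reading, both tests raised at entry, and the hemolysis, alkaline phosphatase and other-cause conditions satisfied. The number of such patients is not given.

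The effect is confined to safety reporting and work-up burden; efficacy endpoints and the dose-limiting toxicity definition are not affected. The text should be corrected, but it does not threaten the trial's conclusions.

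**What to change.** In Protocol 9.5.1, write ULN for LLN in both places:

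- AST/ALT: the smaller of (a) twice baseline, subject to a minimum of 3 × ULN, and (b) 8 × ULN.
- Bilirubin: the smaller of (a) baseline plus 1 × ULN and (b) 3 × ULN.

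Writing the AST/ALT limit this way also removes the two possible readings. Add that a patient with only one test raised keeps the normal-baseline limit for the other (3 × ULN for AST/ALT, 2 × ULN for bilirubin).

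The sponsor's medical lead should confirm the limits and check that no eligible screening values meet the corrected rule; the expected count is 0.

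The cost is a wording change at two places, plus the clarification, in the next amendment. Design, sample size and analysis do not change.

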9.6. Hospitalization

AEs reported from studies associated with hospitalization or prolongations of hospitalization are considered serious. Any initial admission (even if less than 24 hours) to a healthcare facility meets these criteria. Admission also includes transfer within the hospital to an acute/intensive care unit (eg, from the psychiatric wing to a medical floor, medical floor to a coronary care unit, neurological floor to a tuberculosis unit).

Hospitalization does not include the following:

- Rehabilitation facilities;

Investigational Product: IMU-131
Protocol Identifier: IMU.ACS.001
Protocol Version: Protocol Global Amendment #5, 27 September 2023

- Hospice facilities;
- Respite care (eg, caregiver relief);
- Skilled nursing facilities;
- Nursing homes;
- Routine emergency room admissions;
- Same day surgeries (as outpatient/same day/ambulatory procedures).

Hospitalization or prolongation of hospitalization in the absence of a precipitating, clinical AE is not in itself an SAE. Examples include:

Admission for treatment of a preexisting condition not associated with the development of a new AE or with a worsening of the preexisting condition (eg, for work-up of persistent pre-treatment lab abnormality);

- Social admission (eg, patient has no place to sleep);
- Administrative admission (eg, for yearly physical exam);
- Protocol-specified admission during a study (eg, for a procedure required by the study protocol);
- Optional admission not associated with a precipitating clinical AE (eg, for elective cosmetic surgery);
- Hospitalization for observation without a medical AE;
- Pre-planned treatments or surgical procedures should be noted in the baseline documentation for the entire protocol and/or for the individual patient.
- Admission exclusively for the administration of blood products.

Diagnostic and therapeutic non-invasive and invasive procedures, such as surgery, should not be reported as AEs. However, the medical condition for which the procedure was performed should be reported if it meets the definition of an AE. For example, an acute appendicitis that begins during the AE reporting period should be reported as the AE, and the resulting appendectomy should be recorded as treatment of the AE.

9.7. Adverse Event Severity Assessment

9.7.1. Local (injection site) Adverse Event Intensity:

Intensity of the following local AEs should be assessed as described in the table below adapted from the FDA, Center for Biologics Evaluation and Research (CBER), *Guidance for Industry: Toxicity Grading Scale for Healthy Adult and Adolescent Volunteers Enrolled in Preventive Vaccinxe Clinical Trials* dated September, 2007:

Investigational Product: IMU-131
 Protocol Identifier: IMU.ACS.001
 Protocol Version: Protocol Global Amendment #5, 27 September 2023

Table 4: Grading of Local Adverse Event Intensity

Local Reaction to Injectable Product	Absent (Grade 0)	Mild (Grade 1)	Moderate (Grade 2)	Severe (Grade 3)	Potentially Life Threatening (Grade 4)
Pain	Absent	Does not interfere with activity	Repeated use of non- narcotic pain reliever > 24 hours or interferes with activity	Any use of narcotic pain reliever or prevents daily activity	Emergency room (ER) visit or hospitalization
Tenderness	Absent	Mild discomfort to touch	Discomfort with movement	Significant discomfort at rest	ER visit or hospitalization
Erythema/ Redness *	Absent	2.5 – 5 cm	5.1 – 10 cm	> 10 cm	Necrosis or exfoliative dermatitis
Induration/ Swelling**	Absent	2.5 – 5 cm and does not interfere with activity	5.1 – 10 cm or interferes with activity	> 10 cm or prevents daily activity	Necrosis

* In addition to grading the measured local reaction at the greatest single diameter, the measurement should be recorded as a continuous variable.

** Induration/Swelling should be evaluated and graded using the functional scale as well as the actual measurement.

9.7.2. Other Adverse Event Intensity Grading

Patients will be evaluated for safety if they have received any treatment. Adverse events and other symptoms will be graded according to National Cancer Institute's Common Toxicity Criteria for Adverse Events version 4.03 (CTCAE v4.03) in Phase 1b and with version 5.0 (CTCAE v5.0) in Phase 2/Phase 2 Extension.

Table 5: Common Toxicity Criteria for Adverse Events version 4.03 (CTCAE v4.03) and version 5.0 (CTCAE v5.0) Grading

GRADE	Clinical Description of Severity
0	No Change from Normal or Reference Range (This grade is not included in the Version 4.0 or 5.0 document but may be used in certain circumstances.)
1	MILD Adverse Event
2	MODERATE Adverse Event
3	SEVERE Adverse Event
4	LIFE-THREATENING OR DISABLING Adverse Event
5	DEATH RELATED TO Adverse Event

9.8. Causality Assessment

The investigator's assessment of causality must be provided for all AEs (serious and non-serious); the investigator must record the causal relationship in the CRF, as appropriate, and report such an assessment in accordance with the serious adverse reporting requirements if applicable. An investigator's causality assessment is the determination of whether there exists a reasonable possibility that the investigational product caused or contributed to an AE; generally the facts (evidence) or arguments to suggest a causal relationship should be provided. If the investigator does not know whether the investigational product caused the event, then the event will be handled as "related to investigational product" for reporting purposes, as defined by the Sponsor (see [Section 9.12: Reporting Requirements](#)). If the investigator's causality assessment is "unknown but not related to investigational product", this should be clearly documented on study records.

In addition, if the investigator determines an SAE is associated with study procedures, the investigator must record this causal relationship in the source documents and CRF, as appropriate, and report such an assessment in accordance with the SAE reporting requirements, if applicable.

